## GI Perforation Adjudication

Two independent, blinded internal adjudicators along with a third potential tie-breaker adjudicator who are gastroenterologists or who have other highly relevant clinical experience will be utilized to assess potential AEs of acute spontaneous GI perforation.

## Adverse Event Severity and Relationship to Study Drug

The investigator will rate the severity of each AE according to the NCI CTCAE version 5.0, which can be accessed at: [http://ctep.cancer.gov/protocolDevelopment/electronic\\_applications](http://ctep.cancer.gov/protocolDevelopment/electronic_applications).

If no grading criteria are provided for the reported event, then the event should be graded as follows:

**Mild (Grade 1)** Asymptomatic or mild symptoms; clinical or diagnostic observations only; intervention not indicated

**Moderate (Grade 2)** Minimal, local, or noninvasive intervention indicated; limiting age-appropriate instrumental ADL (instrumental ADL refer to preparing meals, shopping for groceries or clothes, using the telephone, managing money, etc.)

### Severe (Grade 3 – 5)

**Grade 3** Severe or medically significant but not immediately life-threatening; hospitalization or prolongation of hospitalization indicated; disabling; limiting self care ADL (self care ADL refers to bathing, dressing and undressing, feeding self, using the toilet, taking medications, and not bedridden)

**Grade 4** Life-threatening consequences; urgent intervention indicated

**Grade 5** Death related to AE

The Investigator will use the following definitions to assess the relationship of the AE to the use of study drug:

**Reasonable Possibility** After consideration of factors including timing of the event, biologic plausibility, clinical judgment, and potential alternative causes, there is sufficient evidence (information) to suggest a causal relationship.

**No Reasonable Possibility** After consideration of factors including timing of the event, biologic plausibility, clinical judgment, and potential alternative causes, there is insufficient evidence (information) to suggest a causal relationship.

## Pregnancy

While not an AE, pregnancy in a study subject must be reported to AbbVie within 1 calendar day after the site becomes aware of the pregnancy. If a pregnancy occurs in a study subject, information regarding the pregnancy and the outcome will be collected.

Female subjects should avoid pregnancy throughout the course of the study, starting with the Screening Visit through 30 days after the last study drug administration. Results of a positive pregnancy test or confirmation of a pregnancy will be assessed starting with the Screening Visit through the final study visit.

Subjects who become pregnant during the study must be discontinued from study drug treatment (Protocol Section 5.5).

The pregnancy outcome of an elective or spontaneous abortion, stillbirth, or congenital anomaly is considered an SAE and must be reported to AbbVie within 24 hours of the site becoming aware of the event.

## 6.2 Toxicity Management

---

The toxicity management of the AEs, including AESIs, consists of safety monitoring (review of AEs on an ongoing basis, and periodic/ad hoc review of safety issues by an independent DMC), and, if applicable, interruption of study drug dosing with appropriate clinical management and/or discontinuation of the subjects from study drug. The management of specific AEs and laboratory parameters is described below.

**Serious Infections:** Study drug should be interrupted if a subject develops a serious infection. Study drug may be restarted once the infection has been successfully treated. Subjects who develop active TB must be permanently discontinued from study drug.

**Herpes zoster:** If a subject develops herpes zoster, consider temporarily interrupting study drug until the episode resolves.

**GI Perforation:** Subjects presenting with the onset of signs or symptoms of a GI perforation should be evaluated promptly for early diagnosis and treatment. Subjects with acute, spontaneous perforation of the GI tract that requires inpatient medical care or urgent surgical intervention (except for appendicitis or mechanical injury) must be permanently discontinued from study drug.

**Malignancy:** Subjects who develop malignancy other than NMSC or carcinoma in situ of the cervix must be permanently discontinued from study drug. Information including histopathological results should be queried for confirmation of the diagnosis. Periodic skin examination is recommended for subjects who are at increased risk for skin cancer.

**Muscle-related symptoms:** If a subject experiences symptoms suggestive of myositis or rhabdomyolysis, consider checking CPK and aldolase with clinical management and/or study drug interruption as deemed appropriate by the treating physician.

**Thrombosis Events:** Subjects who develop symptoms of thrombosis should be promptly evaluated and treated appropriately. If the diagnosis of DVT, pulmonary embolus, or non-neurologic arterial thrombosis is confirmed, the subject must be permanently discontinued from study drug.

**COVID-19:** Interrupt study drug in subjects with a confirmed diagnosis of COVID-19. Consider interrupting study drug in subjects with signs and/or symptoms and suspicion of COVID-19. The COVID-19 eCRF must be completed.

**Management of Select Laboratory Abnormalities:** For any given laboratory abnormality, the investigator should assess the subject, apply the standard of care for medical evaluation and treatment following any local guidelines. Specific toxicity management guidelines for abnormal laboratory values are described in [Table 3](#) and may require a supplemental eCRF to be completed. For subjects with ongoing laboratory abnormalities which require data entry into an eCRF, an additional eCRF related to subsequent laboratory abnormalities is only required if the subject has relevant changes in history (e.g., new onset signs or symptoms) or laboratory values which have returned to normal reference range or its Baseline value followed by subsequent laboratory abnormalities meeting toxicity guidelines (considered a new event). All abnormal laboratory tests that are considered clinically significant by the investigator will be followed to a satisfactory resolution. If a repeat test is required per [Table 3](#), the repeat testing is to occur as soon as possible. Further, repeat testing may be performed at a local laboratory if the subject is unable to use the central laboratory.

**Table 3. Specific Toxicity Management Guidelines for Abnormal Laboratory Values**

Laboratory Parameter	Toxicity Management Guideline
Hemoglobin	
 
If hemoglobin < 8 g/dL, interrupt study drug dosing and confirm by repeat testing with a new sample.
 
If hemoglobin decreases <math>\geq 3.0</math> g/dL from Baseline without an alternative etiology, interrupt study drug dosing and confirm by repeat testing with new sample.
 
If hemoglobin decreases <math>\geq 3.0</math> g/dL from Baseline and an alternative etiology is known or the hemoglobin value remains in the normal reference range, the subject may remain on study drug at the investigator's discretion.
 
If confirmed, continue to withhold study drug until hemoglobin value returns to normal reference range or its Baseline value.
 

ANC	
 
If confirmed <math>< 1000/\mu\text{L}</math> by repeat testing with new sample, interrupt study drug dosing until ANC value returns to normal reference range or its Baseline value.
 
Interrupt study drug if confirmed <math>< 500/\mu\text{L}</math> by repeat testing with new sample. If value returns to normal reference range or its Baseline value, restarting study drug is allowed if there is an alternative etiology identified; documentation should include reason that rechallenge is expected to be safe for the subject. Study drug should be discontinued if no alternative etiology can be found.
 

ALC	
 
If confirmed <math>< 500/\mu\text{L}</math> by repeat testing with new sample, interrupt study drug dosing until ALC returns to normal reference range or its Baseline value.
 

Total WBC count	
 
If confirmed <math>< 2000/\mu\text{L}</math> by repeat testing with new sample, interrupt study drug dosing until WBC count returns to normal reference range or its Baseline value.
 

Laboratory Parameter	Toxicity Management Guideline
AST or ALT	
 
Interrupt study drug if confirmed ALT or AST <math>> 3 \times</math> ULN by repeat testing with new sample and either a total bilirubin <math>> 2 \times</math> ULN or an international normalized ratio (INR) <math>> 1.5</math>.
 
A separate blood sample for INR testing will be needed to measure INR at the time of repeat testing for ALT or AST. A repeat test of INR is not needed for determination if above toxicity management criteria are met.
 
Interrupt study drug if confirmed ALT or AST <math>> 3 \times</math> ULN by repeat testing with new sample along with new appearance of fatigue, nausea, vomiting, right upper quadrant pain or tenderness, fever, rash, and/or eosinophilia (<math>> 5\%</math> increase from Baseline).
 
Interrupt study drug if confirmed ALT or AST <math>> 5 \times</math> ULN by repeat testing with new sample for more than 2 weeks.
 
If ALT or AST <math>> 8 \times</math> ULN, interrupt study drug immediately, confirm by repeat testing with a new sample, and contact the TA MD.
 
 
Subjects with HBc Ab+ (irrespective of HBs Ab status) and negative HBV DNA PCR testing at Screening who develop the following laboratory findings should have HBV DNA PCR testing performed within 1 week (based on initial elevated value):
 
 
ALT <math>> 5 \times</math> ULN OR
 
ALT or AST <math>> 3 \times</math> ULN if an alternative cause is not readily identified.
 
A separate blood sample for HBV DNA PCR testing will be needed at the time of repeat testing for ALT or AST.
 
 
A positive result for HBV DNA PCR testing will require immediate interruption of study drug (unless not acceptable by local practices) and a hepatologist consultation should occur within 1 week for recommendation regarding subsequent treatment.
 
Subjects who meet any of the above criteria should be evaluated for an alternative etiology of the ALT or AST elevation and managed as medically appropriate. If applicable, the alternative etiology should be documented in the eCRF. If ALT or AST values return to the normal reference range or the Baseline value, study drug may be restarted. If restarting study drug, documentation should include reason that rechallenge is expected to be safe. If after clinically appropriate evaluation no alternative etiology for ALT or AST elevation is found or the ALT or AST elevation has not resolved or is not trending down toward normal, the subject should be discontinued from study drug.
 
For any confirmed ALT or AST elevations <math>> 3</math> ULN, complete the appropriate supplemental hepatic eCRF(s).

Serum Creatinine	
 
If serum creatinine is <math>> 1.5 \times</math> the Baseline value and <math>></math> ULN, repeat the test for serum creatinine (with subject in an euvolemic state) to confirm the results. If the results of the repeat testing still meet this criterion, then interrupt study drug and restart study drug once serum creatinine returns to <math>\leq 1.5 \times</math> Baseline value and <math>\leq</math> ULN.
 
 
For the above serum creatinine elevation scenarios, complete the supplemental renal eCRF.

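### Protocol Table 3, AST or ALT row: an elevation that resolves with no alternative cause found meets both the restart sentence and the discontinuation sentence, and no precedence is stated

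*Protocol*

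**What the plan says.** All the transaminase-based interruption triggers in the AST or ALT row of Protocol Table 3 lead into one closing paragraph. It asks for an evaluation for another cause and adds "If applicable, the alternative etiology should be documented in the eCRF". It then gives a restart permission: "If ALT or AST values return to the normal reference range or the Baseline value, study drug may be restarted". The only requirement attached to that permission is "If restarting study drug, documentation should include reason that rechallenge is expected to be safe".

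The discontinuation sentence follows directly. Its first two conditions read "If after clinically appropriate evaluation no alternative etiology for ALT or AST elevation is found or the ALT or AST elevation has not resolved". A third condition covers a value with no downward course, and the stated action under any of the three is to take the subject off study drug.

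Three other places bear on how this is read:

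- **Protocol Table 3, ANC row, the bullet for values below 500/µL.** After recovery, "restarting study drug is allowed if there is an alternative etiology identified"; and "Study drug should be discontinued if no alternative etiology can be found".
- **Protocol Section 5.5.** Immediate discontinuation of study drug is mandatory when laboratory results or adverse events meet the discontinuation criteria of Section 6.2. The restart permission is not mentioned.
- **SAP Appendix A.** One tabulated deviation category is a subject who developed withdrawal criteria and was not withdrawn.

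**The concern.** The restart sentence looks only at whether the value has come back. The discontinuation sentence looks, among other things, at whether a cause was found. These are separate facts about a subject, so both sentences can apply at once. They do so when the value returns to normal or Baseline after interruption and the work-up finds nothing.

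That pattern is compatible with a drug effect, so it is a case the rule ought to settle. Protocol Section 2.2 lists transaminase elevation among the laboratory changes seen with upadacitinib, and hepatic disorders are an adverse event of special interest. With about 35 sites planned, two investigators could act differently on the same facts and each could cite the table.

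For the analysis, the consequence is classification. The same subject could be recorded as a permissible interruption with restart, as a discontinuation of study drug, or as a protocol deviation, depending on which sentence is applied.

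**Working it through.** No stated figure bears on this point and no arithmetic applies. The check applies the two sentences literally, reading each 'or' as inclusive, to every combination of two facts: whether an alternative cause was found, and what the elevation did.

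| Case | Alternative cause found | Course of elevation | Restart sentence | Discontinuation sentence |
|---|---|---|---|---|
| 1 | Yes | Resolved | Permits restart | Not met |
| 2 | Yes | Unresolved, falling | Not reached | Met (not resolved) |
| 3 | Yes | Unresolved, not falling | Not reached | Met |
| **4** | **No** | **Resolved** | **Permits restart** | **Met (no cause found)** |
| 5 | No | Unresolved, falling | Not reached | Met |
| 6 | No | Unresolved, not falling | Not reached | Met |

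**Result.** One of the six cases, case 4, satisfies both sentences. Nothing in the paragraph links them: there is no exception clause and no order of precedence.

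**Can the text resolve case 4?** Only if the reader supplies a rule that the row does not state. There are two candidates:

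- Treat the discontinuation sentence as an exception to the permission. Case 4 is then discontinued.
- Read the first 'or' as 'and', so that discontinuation needs both no cause and no resolution. Case 4 may then restart.

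The two readings give different actions for the same subject.

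**Comparison within the table.** The ANC bullet for values below 500/µL splits recovered subjects by whether a cause was identified, and its two branches do not overlap. This shows only that the overlap is avoidable in drafting. The ANC bullet for values below 1000/µL has no condition on cause, so the ANC row as a whole is not a uniform comparator. Neither bullet shows what the liver rule should be.

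**Link to Section 5.5 and the SAP.** If case 4 meets a Section 6.2 discontinuation criterion, Section 5.5 makes stopping mandatory. A subject restarted under the permission would then fit the SAP Appendix A category for unmet withdrawal. If the permission governs, the same subject is not a deviation. The deviation count depends on an unstated choice.

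**Secondary drafting point.** In the list "no alternative etiology for ALT or AST elevation is found or the ALT or AST elevation has not resolved or is not trending down", any value that is not trending down towards normal is also unresolved. The second limb therefore adds nothing to the first. Its presence suggests that falling values may have been meant to be handled differently, but the text does not say so. No time point is given for judging resolution.

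**The case against.** The strongest reply is that the row can be read without contradiction. A permission followed by a narrower directive is ordinary drafting, and Section 5.5 gives a documentary basis for letting the discontinuation criterion control. That reading is available, and it means that calling the sentences flatly opposite instructions would overstate the point: one says 'may', the other 'should'. What survives is that the row does not state this precedence, and Section 5.5 does not mention restart.

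A second reply is that the investigator's assessment and local standard of care apply generally, and that the sponsor's medical director must be contacted. General discretion does not settle a conflict between two specific sentences. Within this row, contact with the medical director is required only for values above 8 x ULN. For that trigger, differing practice between sites is less likely; the other transaminase triggers have no such step.

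Two stronger inferences are tempting, and the documents do not support them:

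- **That a subject with a known cause and falling but not yet normal values also faces a contradiction.** The restart sentence has not been reached in that case, so only the discontinuation sentence applies (case 2). The wording is unclear, but it is not contradictory.
- **That the ambiguity distorts the comparison of 6, 11 and 22 mg.** No frequency is given, and sites and subjects stay blinded, so the ambiguity would be applied without knowledge of dose. Hepatic safety is also captured through the supplemental hepatic eCRF, the hepatic-disorder category of special interest and the ALT/AST threshold tables in SAP Appendix C, none of which depends on discontinuation counts.

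**Conclusion.** The inconsistency is real and narrow. On the plain wording, a resolved elevation with no alternative cause found is both eligible for restart and due for discontinuation, and neither Table 3 nor Section 5.5 says which prevails. This is more than missing detail, because a written safety rule gives two outcomes for a possible drug-related liver signal.

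Its size is one case in six on the literal reading, in an unknown number of subjects. It bears on subject safety and on consistency between sites. It also bears on the counts of study drug discontinuation and on the SAP Appendix A deviation count. It does not touch the primary or secondary endpoints, the sample size, power or alpha.

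The conclusion rests on two assumptions: each 'or' is inclusive, and no document outside the protocol and SAP, such as site training material, already states the precedence. The redundant wording for unresolved values is a secondary clarification. No view is taken on which clinical rule is right.

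**What to change.** The sponsor's safety physicians should reconcile the two sentences in the AST or ALT row of Protocol Table 3 with each other and with Section 5.5, so that a resolved elevation with no alternative cause found has one stated outcome. In the same edit they should reword the limbs on resolution and trend so that the handling of a falling but not yet normal value is explicit. Which outcome applies in each case is for the sponsor to decide.

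Once the rule is settled, SAP Appendix A can be applied to it as it stands: the reconciled text will determine whether a restarted subject counts as having met withdrawal criteria.

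The cost is a wording change to one table row, with a matching check of Section 5.5, made by amendment or administrative letter. It needs no new procedures, visits or data collection, and no change to the analysis.

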## 6.3 Independent Data Monitoring Committee

---

To ensure subject safety, an external, independent DMC will review unblinded safety data on a cohort level, at approximately 4-month intervals throughout the course of the study, and alert AbbVie to possible safety concerns related to the conduct of the study. The DMC will review safety data to determine if there are any significant safety concerns that would warrant any study action. If necessary to assess benefit/risk, the DMC will also be given access to selected efficacy data.

The DMC charter will describe the roles and responsibilities of the DMC members, frequency of data reviews, and relevant data to be assessed. Communications from the DMC to the Study Team will not contain information that could potentially unblind the team to subject treatment assignments.

# 7 STATISTICAL METHODS & DETERMINATION OF SAMPLE SIZE

## 7.1 Statistical and Analytical Plans

---

The statistical methods provided in this protocol will be focused on primary and secondary analyses. Complete and specific details of the statistical analysis will be described in the Statistical Analysis Plan (SAP).

The primary analysis will be conducted after all subjects have completed Week 24, data pertaining to Period 1 have been cleaned, and a database lock has occurred for the purpose of efficacy and safety analysis in Period 1. The efficacy analysis performed based on this database lock will be the only and final analysis for Period 1.

## 7.2 Definition for Analysis Populations

---

The ITT Population includes all randomized subjects. Subjects will be included in the analysis based on treatment as randomized. The ITT Population will be used for all efficacy analyses.

The following populations will be used for the safety analysis:

- The Safety Population (Safety) is defined as all subjects who are randomized and received at least 1 dose of study drug in the study.
- The all upadacitinib treated (ALL\_UPA) Population is defined as all subjects who received at least 1 dose of upadacitinib in the study. This population will be used to provide a comprehensive summary of safety.

## 7.3 Handling Potential Intercurrent Events for the Primary Endpoint

---

The primary endpoint (Section 3.2) will be analyzed in the ITT Population and no intercurrent events will be considered. All data collected, regardless of premature discontinuation of study drug, will be used in the analysis.

## 7.4 Statistical Analyses for Efficacy

---

The efficacy analysis will be based on the ITT Population and all statistical tests will be performed at a 2-sided significance level of 0.1. The 95% confidence interval of the treatment effect will be provided.

- For continuous variables, comparisons of change and/or percent change from Baseline will be made between upadacitinib and placebo based on the Mixed Model Repeated Measures (MMRM) adjusting for treatment, visit, treatment-by-visit interaction, and stratification factors derived by the actual value (age group [ $\leq 50$  and  $> 50$ ], Baseline disease severity [T-VASI  $< 15$  and  $\geq 15$ ], and status of active vitiligo [Yes/No]) as fixed factors, and Baseline value as a covariate. The MMRM will be the primary approach to handle missing values for continuous endpoints.
- For categorical variables, comparisons will be made between upadacitinib and placebo using the Cochran-Mantel-Haenszel (CMH) test, adjusting for the stratification factors derived by the actual value: age group ( $\leq 50$  and  $> 50$ ), Baseline disease severity (T-VASI  $< 15$  and  $\geq 15$ ), and status of active vitiligo (Yes/No). Non-Responder Imputation incorporating multiple imputation (MI) to handle missing data due to COVID-19 (NRI-MI) will be the primary approach to handle missing values for categorical endpoints.

